Table to Tablet (T2T): A Novel Intervention Framework for Children With Speech Sound Disorders

1st of January 2017

University of Aveiro
Aveiro, Portugal

This study is a randomised control trial. The first step was the creation of partnerships between the University of Aveiro and schools in the Aveiro region (Jesus, Martinez, Valente, & Costa, 2017). Teachers were asked to identify children that they thought had immature or poor speech. All identified children were then assessed (T1). Due to the fact that the project was only selecting children with SSD, most other children (with different diagnoses) were referred to external (to the project) SLPs. The children who fitted the inclusion criteria were then randomly allocated to one of two groups (tabletop or tablet) and were assessed again after a waiting period of 3 months (T2). After this second assessment, the children had intervention and were assessed at post-intervention (T3).

Participants

Twenty-two Portuguese children (four girls and eighteen boys) with phonologically-based SSD, with a mean age of 57 months were selected. This disproportionate number of males-females is a typical distribution (70-80% boys) in the Portuguese population, and has been reported in previous studies (Jesus, Lousada, Domingues, Hall, & Tomé, 2015). Children were assessed and diagnosed as having phonologically-based SSD after an extensive assessment by a Speech and Language Pathologist (SLP), an audiologist and a psychologist.

Participant inclusion criteria were:

- Age range from 3;6 to 6;6;
- European Portuguese as first and only language;
- No impairments on oro-motor structure and function (assessed with the Protocolo de Avaliação Oro Facial – PAOF (Guimarães, 1995);
- No symptoms of verbal dyspraxia;
- Age appropriate receptive language (assessed with the Teste de Linguagem ALPE – TL-ALPE (Mendes, Afonso, Lousada, & Andrade, 2014));
- Audition of 20 dB or lower in the frequencies 500, 1000, 2000 and 4000 Hz;
- Age appropriate non-verbal IQ assessed with the Wechsler Preschool and Primary Scale of Intelligence-Revised – WPPSI-R (Wechsler, 2003);
- Presenting at least two phonological processes at pre-intervention time (Crosbie, Holm, & Dodd, 2005; Dodd, Zhu, Crosbie, Holm, & Ozanne, 2002).

The children's phonological abilities were assessed by a SLP with a single-word naming (67 words) task (Mendes, Afonso, Lousada, & Andrade, 2013). All the children were also assessed for consistency of production. All participants scored below 40% in the Inconsistency Assessment of the Teste Fonético-Fonológico ALPE (Mendes et al., 2013), and were considered to be consistent (Dodd et al., 2002).

Ethical permission was obtained from an independent ethics committee (*Comissão de Ética da Unidade Investigação em Ciências da Saúde – Enfermagem da Escola Superior de Enfermagem de Coimbra*, Coimbra, Portugal) and informed consent was collected from all carers prior to any data collection. The study was also registered at ClinicalTrials.gov.

Intervention

In order to build an intervention that mirrored existing evidence-based and well defined speech and language therapy practice for working with children with SSD (Lousada,

Jesus, Hall, & Joffe, 2014; Lousada et al., 2013), tabletop and digital SSD intervention programmes were developed which incorporated key target areas that have been shown to be effective. These included: (1) Auditory Bombardment (focusing on the target phoneme or phoneme combination) (Hodson & Paden, 1991); (2) Hearing and Discriminating (to incorporate sounds into the phonological system) (Lancaster, 2008); (3) Grapheme-phoneme correspondence (knowledge of phoneme-grapheme relationships) (Gillon & McNeill, 2007); (4) Phoneme identity (to identify phonemes in words) (Gillon & McNeill, 2007); (5) Segmentation (to analyse words at the phonemic level) (Gillon & McNeill, 2007); (6) Blending (to blend isolated sounds together to form words) (Gillon & McNeill, 2007); (7) Rhyme (to identify phonological similarities in spoken word pairs) (Gillon & McNeill, 2007); and, (8) Phoneme manipulation (to analyse and manipulate sounds) (Gillon & McNeill, 2007). The intervention was identical across the two delivery modes: Tabletop and tablet.

There are a total of eighteen different activities grouped by target area (mean number of activities per area of two). As a companion to the activities, homework in the form of a set of games and worksheets were specifically developed for the project. Regular homework is recommended for maximising progress (Gunther & Hautvast, 2010).

Parents/caregivers were invited to be present in therapy sessions either at their child's school or at the clinic, and short homework tasks were given at the end of each session to complete for the following session.

In the tabletop group the homework activities were work sheets focusing on the targeted phonological processes, and in the tablet group, homework was based on four different computerised games.

Each child allocated to the tablet group received a tablet with the games installed at the beginning of the intervention. In each session an information sheet about the game that should be played that week was given to the caregiver.

Furthermore, generalisation tasks for each phonological process were created. These tasks are included to allow SLPs to test if changes in a child's phonological system go beyond the treatment words and targets (Bowen, 2015).

The allocation to one of the interventions (with same content but different delivery method – tabletop or tablet) took place during the waiting period, after the selection process and before the pre-intervention assessment. Each child was given a number from 1 to 22 and randomly allocated to one of the two groups. The numbers were randomised using an online tool (True random integer sequence generator based on atmospheric noise data <https://www.random.org/sequences/>; RANDOM.ORG; Randomness and Integrity Services Ltd).

The phonologically based intervention consisted of a combination of phonological awareness activities (Lousada et al., 2013) adapted from Gillon and McNeill's (2007) phonological awareness programme, Hodson and Paden's (1991) auditory bombardment, and discrimination and listening tasks from Lancaster (2008).

The criteria taken into account to choose the target phonological processes were: Frequency – occurring at least at a 40% rate in the child's speech (Hodson & Paden, 1991); intelligibility (Dodd & Bradford, 2000; Lousada et al., 2014) – less than 2/3 (66%) of the utterances of a child can be understood by unfamiliar listeners (Gordon-Brannan & Hodson, 2000, p. 146); stimulability – including stimuable sounds (Dodd & Bradford, 2000); developmental – earlier acquiring sounds (Dodd & Bradford, 2000; Mendes et al., 2013).

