The activities included were based on a phonological therapy approach. The selection of words used in therapy was based on: Syllabic structure (CV, CVC or CCV) (Brooks & Kempe, 2014); number of syllables (one or two) (Flipsen, 2006); being age appropriate (Fenson et al., 1993); being easily illustrated; and being different from words used for assessment (Lousada et al., 2013; Mendes, Afonso, Lousada, & Andrade, 2013). Words used in therapy were those with which children had difficulty, a criteria used in previous research (Gillon, 2008), and included initial, medial and final word (where applicable) position of the target sound. A list of minimal pair words were selected for *Hearing and Discriminating* and *Phoneme Manipulation*. For the *Rhyme* activity, a list of monosyllabic rhyming words were identified. The criteria used to select these words were: They are all phonologically simple and high frequency, well known by most Portuguese children; two syllable (*Hearing and Discriminating* and *Phoneme Manipulation*) or one syllable (*Rhyme*) words that would rhyme and could be represented by an illustration. Nineteen short stories (one for each phonological process) that used at least twenty words with the target sound were also created, as used by Bowen (2015).

Each target word was illustrated by a professional designer resulting in more than 350 illustrations. A set of three background images was also created (by the same designer) for each short story.

Testing

Assessments of the children with SSD took place at three time points:

- T1 – Baseline and pre-randomisation;
- T2 – Pre-intervention and after a waiting period of 3 months;
- T3 – Post-intervention.

The baseline assessments (T1), pre and post-intervention assessments (T2 and T3), were carried out by the same SLP blind to the study's aims, children allocation and intervention.

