The baseline period occurred between the first assessment at baseline (T1) and the pre-intervention assessment (T2). This period was used to organise all the logistics, schedules and places to deliver therapy (clinic and schools). It was also used to assess the children's non-verbal IQ and hearing. The children did not receive any intervention in this time period. All the children waited three months (the same duration as the intervention) before treatment and therefore acted as their own control (Sadlier, Stephens, & Kennedy, 2008). This period allowed us to see the impact of natural maturation on the children's speech and to compare it to performance after intervention.

The mean PCC scores (Shriberg & McLeod, 1982) were used to compare performance of the two groups. The PCC index is one of the most commonly used indexes to quantify the severity of speech impairment in children with SSD during both evaluation and intervention (Wren, McLeod, White, Miller, & Roulstone, 2013). This quantitative measure is highly sensitive to differences in phonological deficits because it provides information pertaining to the two main error types: Omissions and substitutions (Shriberg, Austin, Lewis, McSweeney, et al., 1997; Shriberg, Austin, Lewis, & McSweeney, 1997).

Although there is evidence that only a small number of children have difficulties producing vowels, Watts (2004) recommends doing a more detailed analysis at this

level using the percentage of vowels correct (PVC) in addition to percentage of phonemes correct (PPC).

Generalisation

After each block of intervention, non-intervention words, which included the process targeted in intervention, were given as generalisation words, in order to assess generalisation to non-targeted words (Palle, Berntsson, Miniscalco, & Persson, 2012). The words were selected based on the phonological process trained. They were different from those used during intervention but targeted the same phonological processes and were a close match in terms of production difficulty, frequency in the Portuguese language and syllable structure.

Each child had five opportunities to produce the correct target. These words were used to determine if the child generalised the targeted speech skill and provide important insight into the impact of intervention on a child's phonological system (Baker & McLeod, 2004).

Reliability

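### Does the two-process inclusion criterion, worded for the pre-intervention assessment, remove children after randomisation and bias the waiting-versus-therapy comparison?

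*Combined protocol and SAP*

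**What the plan says.** All references are to the combined protocol and SAP.

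- **Participants, last inclusion criterion:** "Presenting at least two phonological processes at pre-intervention time".
- **Testing, list of assessments:** the first is "T1 – Baseline and pre-randomisation" and the second is "T2 – Pre-intervention and after a waiting period of 3 months".
- **Opening design paragraph:** "The children who fitted the inclusion criteria were then randomly allocated to one of two groups", with the T2 assessment following after the wait.
- **Intervention, allocation paragraph:** allocation "took place during the waiting period, after the selection process and before the pre-intervention assessment". The children were numbered 1 to 22 for the draw.
- **Testing, baseline-period paragraph:** the wait was also used to assess "non-verbal IQ and hearing", both of which are inclusion criteria. Each child served as its own control, with change over the wait set against performance after therapy.
- **Reliability:** two children were re-transcribed at each of T1, T2 and T3, and this is given as 9% of the speech samples.

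**The concern.** If pre-intervention time means T2, the criterion can be checked only after allocation. A child who had fallen below two processes by then would be excluded after randomisation.

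Three things would be at stake. First, the excluded children would be those with good T2 scores. The children kept would include some whose T2 score was low by chance and who drift back up by T3. The waiting gain would be understated and the therapy gain overstated, both in favour of therapy in the own-control comparison. Second, the randomised set would no longer be intact, in a trial of only 22. Third, IQ and hearing were checked in the same interval as allocation, so eligibility on those criteria might also have been settled after the draw.

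**Working it through.** **1. Order of events.** Four statements bear on it.

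| Place | What it implies |
|---|---|
| Inclusion criterion, read with the T2 label | Eligibility completed at T2, after allocation |
| Design paragraph | Criteria met, then allocation, then T2 |
| Allocation paragraph | Selection, then allocation, then T2 |
| Assessment list | T1 is the pre-randomisation assessment |

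The first conflicts with the second and third. It is a single phrase, which can also mean simply before treatment.

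The IQ and hearing checks conflict with nothing. They fall in the wait, and so does allocation, but allocation is placed after selection. The Participants section says diagnosis followed assessment by the speech and language pathologist, the audiologist and the psychologist. All of this holds if the checks came early in the wait and the draw followed.

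**2. Was anyone removed?** Twenty-two were selected and 22 were numbered. The 9% in the Reliability section gives a further check, because a child removed at T2 would have no T3 sample.

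- Per assessment point: 2/22 = 9.1%; 2/21 = 9.5%, which rounds to 10%; 2/20 = 10%.
- Pooled over three points: none missing, 6/66 = 9.1%; one child without T3, 6/65 = 9.2%; two without T3, 6/64 = 9.4%; three without T3, 6/63 = 9.5%, which rounds to 10%.

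The natural, per-point reading gives 22 children at T3. The pooled reading would allow at most two missing. Both assume conventional rounding.

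**3. Size of the bias if children were removed.** The documents give no variance, no correlation and no share failing at T2, so these are assumptions. Take T1, T2 and T3 as jointly normal with SD 1 and common correlation r, and remove the best-scoring share q at T2. With z the upper-q normal quantile:

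- λ = φ(z)/(1 − q)
- shift in waiting gain = −(1 − r)λ; shift in therapy gain = +(1 − r)λ
- shift in therapy gain minus waiting gain = 2(1 − r)λ

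| Removed of 22 | q | λ | r = 0.7 | r = 0.8 | r = 0.9 |
|---|---|---|---|---|---|
| 0 | 0 | 0 | 0 | 0 | 0 |
| 1 | 4.5% | 0.0956/0.9545 = 0.100 | 0.06 | 0.04 | 0.02 |
| 2 | 9.1% | 0.1636/0.9091 = 0.180 | 0.11 | 0.07 | 0.04 |

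Larger shares give larger figures (q = 20%, r = 0.8: 2 × 0.2 × 0.350 = 0.14 SD). That would be about four of the 22, which the 9% does not support. The rule counts processes while the outcome is the percentage of consonants correct (PCC). The table treats the two as perfectly correlated and so overstates the effect.

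**4. Would applying the rule at T1 help?** A simulation of 4 million children assumed a true waiting gain of 0.15 SD, a true therapy gain of 0.60 SD (difference 0.45) and r of 0.8 or 0.9, with two cut-offs.

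| Selection | Waiting gain | Therapy gain | Error in the difference |
|---|---|---|---|
| T1 only | 0.18 to 0.31 | 0.60 | −0.03 to −0.16 |
| T1 and T2 | 0.11 to 0.14 | 0.63 to 0.73 | +0.04 to +0.16 |

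For example, with r = 0.8 and the stricter cut-off: 0.60 − 0.31 − 0.45 = −0.16, and 0.725 − 0.113 − 0.45 = +0.16. Children were in any case picked for poor speech at T1. Under these assumptions, moving the rule exchanges one error for another of similar size and opposite sign.

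**5. The randomised comparison.** In every case simulated, the tabletop-tablet difference in T2-to-T3 gain stayed within 0.002 SD of zero. No therapy precedes T2 and its assessor is blind to allocation, so removal at T2 has no reason to favour an arm.

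**The case for a change.** The literal reading has real support. The document consistently uses the pre-intervention label for T2. Each child has two therapy blocks aimed at different phonological processes, which is a practical reason to want two processes present when therapy starts. Nothing says what happens to an allocated child who no longer has two. Arm sizes and numbers analysed are not stated, so post-randomisation exclusion cannot be strictly ruled out. The 9% could have been truncated, or computed on the number randomised. If children were removed, the overstatement of the therapy gain survives even when T1 selection is allowed for.

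The wording conflict therefore stands, and so does the direction of bias on therapy gain, conditional on removal. The claim that the rule biases the results does not stand, because it needs removals that nothing in the document reports or provides for. A T2 threshold also acts on level, not on change: a mild case near the cut-off would go, while a severe case with a large gain would stay. It would not pick out exactly the children who matured most.

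**Conclusion.** This is a clerical slip in one timing phrase. The sequence of selection, allocation and T2 is stated in two other places, and the count of 22 is the same at selection and at numbering. The reliability percentage agrees with 22 at every assessment.

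On that reading the bias is zero. If one child had been removed, the own-control contrast would shift by about 0.02 to 0.06 SD; if two, by about 0.04 to 0.11 SD. Both ranges take r from 0.9 down to 0.7 and are upper figures, because the criterion is not PCC itself. The tabletop-tablet comparison is not biased in either case.

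Moving the criterion to T1 brings no gain in the own-control contrast. The document already reports post-treatment transcription reliability, so selection is complete and rewording the criterion would alter no result. An analyst would take the 22 allocated children as the analysis set, and the usual account of numbers per arm in the report would confirm it. The conclusion rests on conventional rounding of the 9% and on there being no unreported exclusion at T2.

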The production of all isolated words of two randomly selected children from the three assessment periods (baseline, pre- and post-treatment) were annotated and transcribed by a trained SLP not involved in the study and blind to its aims. Point-to-point reliability was 95.52% (baseline assessment – T1), 94.74% (pre-treatment assessment – T2) and 96.46% (post-treatment assessment – T3). These values are comparable with those reported in other studies in disordered child phonology (Shriberg, Tomblin, & McSweeny, 1999; Shriberg & Lof, 1991) and were considered adequate for the objective of this study. Two children (for each assessment point) represents 9% of speech samples and this percentage is equivalent to what is reported when checking

reliability in other effectiveness studies (Crosbie et al., 2005; Dodd & Bradford, 2000; Lousada et al., 2014; Lousada, Jesus, Capelas, et al., 2013).

Data analysis / statistics

Non-parametric Wilcoxon and Mann-Whitney tests were used to compare data between groups and time periods and multi-comparisons corrections for type-one errors have been made using Bonferroni's correction for every pair of comparisons involving both tabletop and tablet groups. Effect sizes were calculated using Cohen's d with the bias correction given by Hedges's g for the independent samples case (Lakens, 2013). For the purpose of interpreting the effect sizes, the following commonly used benchmarks were used (Field, 2017): Small ($d=0.2$), medium ($d= 0.5$), and large ($d=0.8$). The statistical analysis was made using IBM SPSS Statistics version 22. The level of significance used was 0.05.

References

- Allen, M. M. (2013). Intervention Efficacy and Intensity for Children With Speech Sound Disorder. *Journal of Speech Language and Hearing Research*, 56(3), 865. [https://doi.org/10.1044/1092-4388\(2012/11-0076\)](https://doi.org/10.1044/1092-4388(2012/11-0076))
- Baker, E., & McLeod, S. (2004). Evidence-based management of phonological impairment in children. *Child Language Teaching and Therapy*, 20(3), 261–285.
- Bowen, C. (2015). *Children's Speech Sound Disorders* (2nd ed.). Oxford: Wiley-Blackwell.
- Brooks, P., & Kempe, V. (2014). *Encyclopedia of Language development*. New York: SAGE.

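### Allocation is not balanced on severity and the tabletop-versus-tablet PCC comparison has no baseline term, so chance imbalance goes uncorrected and precision is lost

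*Combined protocol and SAP*

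**What the plan says.** The Participants section gives the sample: "Twenty-two Portuguese children (four girls and eighteen boys) with phonologically-based SSD". The Intervention section places allocation in time (it "took place during the waiting period, after the selection process and before the pre-intervention assessment") and describes the method: "Each child was given a number from 1 to 22 and randomly allocated to one of the two groups". It adds: "The numbers were randomised using an online tool (True random integer sequence generator based on atmospheric noise data". Group sizes are not given, and no stratification, matching or minimisation on severity or age is described.

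The Testing section labels the first assessment "T1 – Baseline and pre-randomisation". The same section says that mean PCC scores "were used to compare performance of the two groups".

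Under Data analysis / statistics the test is named: "Non-parametric Wilcoxon and Mann-Whitney tests were used to compare data between groups and time periods". Effect sizes are Cohen's d with Hedges's correction for independent samples. Bonferroni correction and a 0.05 level are stated. No baseline-adjusted comparison is described, and the text does not say whether the Mann-Whitney test is applied to raw T3 PCC or to change.

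**The concern.** Severity at the start is likely to predict PCC three to six months later better than anything else recorded here. There are two places to deal with it: at allocation, by balancing, or in the analysis, by adjustment. The plan as written does neither. With 22 children, a chance difference in starting severity can create or mask an apparent difference between delivery modes. The child-to-child variation that baseline PCC could explain also stays in the error term.

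The second cost matters more, because it is paid in every realisation of the trial and not only in the unlucky ones. The two arms are meant to share content and differ only in how materials are presented, so the true contrast may well be modest. The waiting period, in which children act as their own controls, helps to separate maturation from treatment within a child. It does not adjust tabletop against tablet.

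**Working it through.** The documents give no sample-size, power or imbalance figure, so there is none to reproduce.

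**Inputs from the documents.** 22 children; T1 before allocation; Mann-Whitney test; level 0.05; benchmarks of 0.2, 0.5 and 0.8 SD for small, medium and large.

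**Assumptions.** 11 v 11; roughly normal PCC with the same SD at baseline and T3; baseline-to-T3 correlation r from 0.5 to 0.9; two-sided 0.05 before Bonferroni correction, because the number of comparisons is not stated. Differences are in between-child SDs of PCC.

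**1. Size of the chance gap D.** Its SD is sqrt(1/11 + 1/11) = 0.426, and P(|D| > t) = 2[1 − Φ(t/0.426)].

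| t (SD) | P(\|D\| > t) |
|---|---|
| 0.2 | 64% |
| 0.3 | 48% |
| 0.5 | 24% |
| 0.8 | 6% |

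The median |D| is 0.29 SD. A coin toss per child, with unequal groups allowed, gives 65%, 49%, 25% and 7%.

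**2. Carry-over into the comparison.** With no true effect, the expected group difference given D is r·D for raw T3 and (r − 1)·D for change. For D = 0.5 and r = 0.7, 0.8, 0.9:
- raw T3: 0.35, 0.40, 0.45 SD;
- change: −0.15, −0.10, −0.05 SD, that is, smaller and in the opposite direction.

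**3. Mann-Whitney rejection rate with no true effect (simulation).**

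| r | Raw T3, all trials | Raw T3, given \|D\| > 0.5 | Change, given \|D\| > 0.5 |
|---|---|---|---|
| 0.7 | about 5% | 13% | 8% |
| 0.8 | about 5% | 15 to 16% | 7% |
| 0.9 | about 5% | 18% | 5 to 6% |

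Over all trials, the rate for change is also about 5%.

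**4. Standard error of the group difference, allocation left as it is.**
- Raw T3: 0.426, by simulation 0.43.
- Change: 0.426 × sqrt(2 − 2r).
- ANCOVA: 0.426 × sqrt(1 − r²) × sqrt(1 + 1/18). The last factor is the cost of estimating the slope from 22 children. At r = 0.7 this is 0.426 × 0.714 × 1.027 = 0.31.

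| r | Raw T3 | Change | ANCOVA |
|---|---|---|---|
| 0.5 | 0.43 | 0.43 | 0.38 |
| 0.7 | 0.43 | 0.33 | 0.31 |
| 0.8 | 0.43 | 0.27 | 0.26 |
| 0.9 | 0.43 | 0.19 | 0.19 |

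**5. Detectable difference with 80% power** (normal approximation, without the slope cost, so slightly optimistic). Raw T3: (1.96 + 0.84) × 0.426 = 1.19 SD. ANCOVA: 1.19 × sqrt(1 − r²) = 1.03, 0.85, 0.72 and 0.52 SD at r = 0.5, 0.7, 0.8 and 0.9. Power for a difference of 0.8 SD rises from 47% to 58%, 75%, 88% and 99%.

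**6. Balancing the allocation instead.** Randomising within 11 adjacent pairs ranked on T1 PCC cuts the SD of D from 0.43 to 0.10; a median split cuts it to 0.30. Pairing without a covariate gives standard errors of 0.31, 0.27 and 0.21 at r = 0.7, 0.8 and 0.9. Pairing with ANCOVA gives 0.31, 0.26 and 0.19, the same as ANCOVA under the existing allocation.

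**The case against.** Randomisation without balancing on prognosis is a legitimate choice, and the planned test is valid. Its type I error over all allocations is about 5%, and the 13 to 18% figure describes only the unlucky quarter of allocations, before a Bonferroni correction that would lower it. If the test is applied to change, most of the harm and most of the precision loss disappear at high r. All of this stands. It limits the size of the point but does not remove it. The plan does not say that change is tested, and a change score still gives up precision at moderate r (0.43 against 0.38 at r = 0.5).

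A reader might infer more than the documents support:
- **That allocation was unrestricted.** A random ordering of the numbers 1 to 22 suggests a shuffled list cut in two, which would fix the group sizes. What is missing is balance on severity.
- **That a sizeable imbalance is likely.** Only a gap above the plan's small benchmark is more likely than not. A gap above the medium one has about a 1-in-4 chance.
- **That any imbalance passes whole into the result.** That is so only for raw T3, and then multiplied by r.
- **That T1 PCC was in hand at allocation.** The T1 assessment came first, but PCC required offline transcription and entry into the analysis tool. The documents do not say that this was finished in time.

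**Conclusion.** The point holds as a recommendation about the analysis. Baseline severity enters neither the allocation nor the between-group comparison, and adjusting for it would use data already collected. Against a raw T3 comparison, adjustment reduces the standard error by about 12% at r = 0.5 (0.38/0.43) and by about 56% at r = 0.9 (0.19/0.43). Against a change score the gain is small at high r. It also removes the conditional bias in allocations that happen to be unbalanced.

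It would be wrong to conclude that the randomisation is invalid, that the false-positive rate is inflated overall, or that the children should have been re-randomised: the precision comes from the analysis. The figures rest on the 11 v 11 split, near-normal PCC with equal SDs, and assumed correlations, none of which the documents report.

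**What to change.** In Data analysis / statistics, name one main tabletop-versus-tablet comparison: T3 PCC by group, adjusted for pre-intervention PCC, by ANCOVA or rank ANCOVA. Choose T2 or T1 as the covariate before the comparison is run. T2 is closer to T3 and precedes any treatment, although it follows allocation; T1 is strictly pre-randomisation. Report the adjusted difference with a confidence interval alongside Hedges's g. State whether any retained Mann-Whitney test uses raw T3 or change. Report group sizes and baseline PCC by group.

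The cost is one degree of freedom and a linearity assumption, which the rank version eases. No new data are needed.

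Pairing or stratifying on severity is optional. It applies only if allocation is still open, whereas the text describes it as done, and only if T1 PCC is scored by then. A strictly paired analysis would also lose a whole pair, out of 11, for each child who drops out. Once baseline PCC is in the analysis, balanced allocation adds little.
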